Dextromethorphan in Fibromyalgia Statistical Analysis Plan

NCT #: NCT03538054

ID: F161018005

Version Date: 6/28/2022

Statistical Analysis Plan

Statistical analyses were performed in SAS software, Version 9.4 of the SAS System for Windows (SAS Institute Inc., Cary, NC, United States). The primary outcome was the difference in daily self-reported general pain during the last four weeks of placebo versus the last four weeks of DXM treatment. Normality testing was performed with Shapiro–Wilk tests. Participant outcome scores were meancentered by participant, allowing analyses to reflect within-person changes to the treatments, rather than between-person differences. A generalized estimating equations (GEE) model is fitted to predict daily symptom severity based on study condition (placebo, DXM), assuming the autoregressive correlation structure and normal distributions. The grouping variable was subject ID. Significance of the parameter estimates was assumed at p<0.05. There were no corrections for multiple comparisons.

The secondary outcome (self-reported physical activity) was tested using the same GEE approach. Additionally, exploratory analyses (highest pain, muscle pain, fatigue, and depressed mood) were tested in separate GEEs.

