Individuals who satisfy the telephone pre-screening criteria will be invited to a comprehensive in-person screening session. These sessions will be conducted by the PI or trained research staff. Individuals will first undergo informed consent; the consent form will describe the necessary eligibility confirmation that takes place before proceeding with the full study. Consenting individuals will complete several self-report questionnaires, submit to an examination of their height, weight, and vital signs (blood pressure, heart rate, and temperature), and provide a blood sample to ensure eligibility per the study criteria. Participant will receive a hand held tablet and instructions on how to complete the daily questions via the tablet. Vital signs & blood draws will be taken by the CRU nursing staff, using standardized sterile techniques.

Once the blood test results are available from the UAB Hospital Lab they will be reviewed by the PI and study doctor to confirm eligibility. All eligible participants will be contacted by telephone by a member of the research staff. If a participant's test results do not meet eligibility criteria, the individual will be informed that they are ineligible to participate and asked to return the handheld tablet to the research team. Alternatively, potential participants will be given a self-addressed envelope to return the tablet if they are unwilling to return to the site.

Visit 2

Participants will return to the CRU or Campbell Hall after approximately 14 days following visit 1. At this visit, a member of the study team will conduct an open interview to review the daily at-home symptom reporting and general health since the first visit. Also at this time the study team will instruct the participants on how to take their study medication. The placebo will be purchased from a compounding pharmacy such as Double Oak Pharmacy in Birmingham, Alabama. The participants will receive their initial 5 weeks supply of medication, which is placebo (single-blind). Participants will not be told when they are taking placebo or DXM until the end of study. The participants will also continue to record their symptoms twice a day using the hand-held device throughout the duration of the study for the entire (~20 weeks).

Visit 3

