Approximately 5 weeks after visit 2, the participant will return to the CRU so the nursing staff can record their vital signs and discuss any adverse events. The study staff will review their at home daily symptoms and receive DXM for approximately the next 5 weeks.

Visit 4

Approximately 5 weeks after visit 3, the participant will return to the CRU so the nursing staff can record their vital signs and draw 20cc of blood. The blood will be analyzed by the UAB Hospital lab to monitor the participant's liver & renal function. Also, at this visit the research team will review daily at-home symptoms & any adverse events. If any participant has experienced serious/severe adverse events the participant will be terminated from the study as to ensure there is no increased harm to the participant. If no adverse events have

been experienced the participant will receive the next dose of DXM to take for 5 weeks, and continue the athome daily symptom review using the hand-held device.

Visit 5

Approximately 5 weeks after visit 4, the participant will return to the CRU so the nursing staff can record their vital signs and draw 20cc of blood. The blood will be analyzed by the UAB Hospital lab to monitor the participant's liver & renal function. Also, at this visit the research team will review daily at-home symptoms & any adverse events. If any participant has experienced serious/severe adverse events the participant will be terminated from the study as to ensure there is no increased harm to the participant. If no adverse events have been experienced the participant will receive the normal dose of DXM to take for 30 days and continue the at-home daily symptom review using the hand-held device.

Visit 6

Approximately Two weeks after visit 5 the participant will return to the CRU or Campbell Hall to turn in their handheld device and have their final interview with the research staff. At this visit, [name] will review daily symptoms and general health since visit 10 and un-blind the participant to which medications were received during the study.

A +/- 3 day study visit window will be implemented for all study visits to allow for reasonable flexibility in the participant's schedule as well as staff availability.

At any time throughout the study, if a participant reports feeling unwell or having any adverse events from any of the supplements, a review will be conducted by the PI and study doctor. If necessary, appropriate medical management will be provided.

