If any participant is terminated from participating in the study, they will be required to return the hand-held device and any unused medicine back to a member of the UAB research study staff.

Study Timeline

The participant will be involved approximately 20 weeks for the entire study; this includes the in person screening, daily symptom reporting which is 10 minutes per day or less, and study medication disbursement. All blood draws will be conducted at the CRU in Jefferson Towers. Study medication disbursement will occur at UAB Campbell Hall or CRU.

Week	Task	Visit		Money
1	Screening	V1	Blood Draw Screening Labs & assays	\$50
2	Baseline			
3	Baseline	V2		\$100.00
4	Placebo			
5	Placebo			
6	Placebo			
7	Placebo			
8	Placebo	V3		\$100.00
9	DXM			
10	DXM			
11	DXM			
12	DXM			

13	DXM	V4	Blood Draw Hepatic / Renal & Assays	\$100.00
14	DXM			
15	DXM			
16	DXM			
17	DXM			
18	DXM	V5	Blood Draw Hepatic / Renal & Assays	\$100.00
	Baseline no			
19	drug			
	Baseline no			
20	drug	V6	Blood for assays	\$100.00
			Total Compensation	\$550.00

Compensation

Participants will be compensated with cash at screening, and check or direct deposit at all remaining visit. Cash is necessary at the screening visit as it will allow for most exclusionary criterion to be detected. Participants can receive up to \$550 in compensation for completing the study:

- Visit 1 (in-person screening): \$50
- Visits 2-6: \$100

Biospecimens

Peripheral blood samples will be collected and appropriately processed by the Clinical Research Unit (CRU) staff.

Screening session protocol: A 21/23g needle will be used to collect a maximum of 60cc of blood into labeled blood collection tubes to conduct screening tests. This blood will be tested by the UAB Hospital Lab to ensure that the participant meets the study criteria. The screening tests will include: complete blood count, erythrocyte sedimentation rate, thyroid stimulating hormone, free thyroxine, c-reactive protein, antinuclear antibodies, rheumatoid factor, liver function tests, kidney function tests and human chorionic gonadotropin. The total amount of blood drawn per participant for all study visits is 120cc.

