Participants should not take Dextromethorphan (DXM) if they have been diagnosed with phenylketonuria (PKU) because it could contain phenylalanine, if they are currently using or have used an MAO inhibitor, or if they have one of the following conditions: chronic bronchitis, emphysema, asthma, diabetes, liver disease, and mucus with cough or slowed breathing. These will be reviewed at the during the phone screen, in person screening and throughout the study. Dextromethorphan is known to produce side effects in individuals which include: slight drowsiness / dizziness, nausea or vomiting. Rarely, severe drowsiness can occur, participants will be instructed to notify study staff if they experience any of these side effects.

Grapefruit juice interacts with Dextromethorphan, participants will be asked to not drink grapefruit juice for the duration of the study.

Dextromethorphan is known to produce side effects in individuals which include: diarrhea, dizziness, cough, vomiting, swelling in the hands, ankles and or feet. Rarely slight drowsiness can occur; participants will be instructed to notify study staff if they experience any of these side effects. The most severe possible complication is serotonin toxicity.

The participant may experience some discomfort, bruising and the possibility of infection at the site of the blood draw on visits 1,3,6,9. Bruising should be minimal and should go away with a 2-3 days of the blood draw. We will minimize these risks by having only certified nurses or trained phlebotomist conduct the blood draws using standard sterile techniques.

The risks associated with taking the study medications can be primarily be avoided through proper screening of the participant and having a clear understanding of the medication the participant takes, educating the participant to contact the study staff of any and all changes to their medication. If an adverse event or side effect arises, a determination of severity and proper medical care will be advised and depending on the severity of the symptom the participant would be removed from the study and an evaluation of how to continue would be made by the study staff.

Minimization of Risks

Our screening procedures will minimize the probability of enrolling a patient who has a greater than normal risk of suffering adverse events from the medication (DXM). Any remaining risks for adverse events will be reduced by several checks:

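### The SAP centres scores by participant but not the placebo/DXM indicator, so its coefficient is guaranteed to be the within-person change only when analysed participants have equal shares of DXM-window days

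*SAP*

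**What the plan says.** The SAP defines the primary outcome as "the difference in daily self-reported general pain during the last four weeks of placebo versus the last four weeks of DXM treatment". On preparing the scores it says: "Participant outcome scores were meancentered by participant, allowing analyses to reflect within-person changes to the treatments, rather than between-person differences". The GEE is then "fitted to predict daily symptom severity based on study condition (placebo, DXM), assuming the autoregressive correlation structure and normal distributions", grouped by subject ID. Neither centring of the condition indicator nor participant effects are mentioned. The SAP does not say which days form each participant's mean, who is analysed, or how the DXM window is set for someone who leaves early.

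The protocol fixes the order of treatments. Under Visit 2: "The participants will receive their initial 5 weeks supply of medication, which is placebo (single-blind". In the Study Timeline table, placebo fills weeks 4-8 and DXM weeks 9-18. The Visit 4 and Visit 5 sections provide for termination after serious or severe adverse events. The Risks section is not tied to a visit: "depending on the severity of the symptom the participant would be removed from the study". The end of Study Visits adds: "If any participant is terminated from participating in the study, they will be required to return the hand-held device". Diary data therefore stop when the participant leaves.

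**The concern.** Subtracting each participant's mean removes between-person differences from the outcome. If the predictor is left as it is, it still varies between participants whenever their shares of DXM days differ. That variation enters the denominator of the slope, but the centred outcome has nothing left to match it, so the slope is too small. Because placebo comes first, early leaving removes DXM days and not placebo days, which is how such imbalance would arise here.

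At stake is the size of the primary effect, which the SAP defines as a difference. Under the conditions below, part of that size would be set by how many participants left early and not by the drug. The secondary outcome uses the same approach. For the exploratory outcomes the SAP says only that separate GEEs are fitted, so the point applies to them only if they too are centred.

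**Working it through.** The documents give no effect size, SD, power or dropout rate, so there is no planned figure to reproduce.

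**Inputs from the documents.** 15 participants (protocol, Participants). Windows of four weeks, or 28 days, each (SAP). By the timeline table these are weeks 5-8 for placebo and weeks 15-18 for DXM, with weeks 9-14 (42 days) between them.

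**Assumed.** k = 1, 3 or 5 leavers, each with 28 placebo days and m DXM-window days; one score per day; a constant true effect; dropout unrelated to outcome.

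**1. Window-day centring, working independence.** The share of the true effect recovered is W/T, where W is the within-participant and T the total sum of squares of the indicator.
- A completer contributes 28×28/56 = 14 to W. A leaver contributes 28m/(28+m).
- T = N0×N1/(N0+N1), with N0 = 15×28 = 420 and N1 = 28(15−k) + mk.
- All complete: W = 15×14 = 210 and T = 420×420/840 = 210, so the share is 1.000.
- k = 3, m = 0: W = 12×14 = 168 and T = 420×336/756 = 186.7, so the share is 0.900. For m = 0 the formula reduces to 1 − k/30.

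| DXM-window days per leaver | k = 1 | k = 3 | k = 5 |
|---|---|---|---|
| 0 | 0.967 | 0.900 | 0.833 |
| 7 | 0.985 | 0.958 | 0.933 |
| 14 | 0.995 | 0.985 | 0.978 |
| 21 | 0.999 | 0.997 | 0.996 |

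**2. Autoregressive working correlation, m = 0.** These shares come from solving the GEE normal equations for the expected slope.
- Records treated as consecutive: 0.970, 0.909, 0.847 at rho 0.5, and 0.993, 0.978, 0.961 at rho 0.9.
- The 42-day gap kept: 0.967, 0.900, 0.833 at rho 0.5, and almost the same at rho 0.9 (0.834 for k = 5).

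**3. All-days centring, working independence.** Assume 14 baseline, 35 placebo, 70 DXM and 14 no-drug days for a completer. Assume 14, 35 and 35 days (baseline, placebo, DXM) for a leaver at Visit 4, and calendar windows, so that leavers have no DXM-window days. Set placebo level 0, DXM level −1, baseline b and no-drug level w. The completer mean is Mc = (14b − 70 + 14w)/133 and the leaver mean is Ml = (14b − 35)/84. The share is 1 + (k/15)(Mc − Ml). For k = 3:
- b = w = 0: 1 + 0.2(−0.526 + 0.417) = 0.978
- b = 2, w = 0: 1 + 0.2(−0.316 + 0.083) = 0.954
- b = w = 2.5: 1.000
- b = 0, w = 2: 1 + 0.2(−0.316 + 0.417) = 1.020

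The direction therefore depends on levels that the documents do not give.

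**4. Effect on significance.** This was a GEE simulation with window-day centring, m = 0 and 300 trials per k. All inputs were assumed: effect 0.6 scale points, residual SD 1.5, between-person SD 1.5, SD of the effect 0.5, rho 0.5, 10% missed days, calendar gap kept, robust standard errors. The figures compare the SAP as written with condition also centred, for k = 1, 3, 5.
- Estimate ratio: 0.966, 0.900, 0.834. Standard error ratio: 0.972, 0.913, 0.850.
- Ratio of test statistics (first divided by second): 0.994, 0.986, 0.981.
- Shift in the estimate: 0.10, 0.26, 0.39 of a standard error.
- Rejection rates: 79.3% against 79.7%, 71.7% against 72.7%, and 60.0% against 61.0%. The significance verdict differed in 1% of trials.

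**5. After the fix.** With condition also centred, or with participant fixed effects on uncentred scores, the expected share is 1.000 in every case computed.

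**The case against.** The strongest reply is that several conditions must hold together: participants leave before supplying a full DXM window, they are still analysed, and centring uses window days. None is established. The last four weeks of DXM can naturally be read as each participant's own last four. A Visit 4 leaver, with about five DXM weeks, then has a full window and causes no distortion. Leaving after 21 DXM days costs at most 0.4% for k = 5. If participants with only one window are excluded, the zero-day row of the table disappears and only the loss from partial windows remains. Missed diary days alone do little: about 15% missing at random with no leavers gives 0.997. The 0.83 is an extreme assumed case. No target effect is stated against which a loss of a few percent could be judged.

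All of this stands and limits the point to a conditional one. It does not remove it, because the SAP leaves the analysis set, the centring days and the window rule open while claiming a within-person estimate.

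A reader might infer three stronger things that the documents do not support. First, that the trial's result is biased: no dropout figure or analysis set is given. Second, that any inequality of windows understates the effect: under all-days centring the share ran from 0.954 to 1.020. Third, that centring condition cures dropout bias: the 1.000 rests on dropout unrelated to response, whereas the removal described under Risks is driven by symptoms.

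**Conclusion.** The point holds as a minor, conditional one. The centring described guarantees the claimed within-person estimate only when analysed participants have equal shares of DXM-window days. If participants without DXM-window days are kept and centring uses window days, the effect shrinks by about 3% for each one out of 15. The loss is less if they have some DXM days, or if records are treated as consecutive with high autocorrelation. With 14 of 28 days it is 0.5%, 1.5% or 2.2% for 1, 3 or 5 leavers. It is nil when windows are equal.

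Only the reported effect size is at issue, since the standard error shrinks almost in step. The figures rest on the assumed number of leavers, a constant effect and dropout unrelated to outcome.

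A separate matter bears on the window itself. The protocol's Visit 5 section says "the participant will receive the normal dose of DXM to take for 30 days", while the timeline table shows no drug in weeks 19-20 and Visit 6 falls about two weeks after Visit 5. These passages must be reconciled before the last four weeks of DXM can be fixed even for completers. This conflict is not evidence of a centring fault.

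**What to change.** In the primary and secondary models, and in the exploratory models if they are also centred, centre the condition indicator by participant over the same analysed days as the outcome. Alternatively, fit participant fixed effects to uncentred scores. State in the SAP which days form the mean, how the DXM window is defined for early leavers, and that participants with only one window do not inform the treatment estimate. Reconcile the Visit 5 text with the timeline table.

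The cost is one line of SAS code, a re-run of the models and two or three sentences; no new data are needed. Results do not change if all analysed participants have equal windows. There are two downsides. Single-window participants no longer contribute to the estimate, and the standard error rises with the estimate (0.227 against 0.207 in the simulation with 3 leavers). The change removes the centring distortion but not any bias from dropout related to response, which would need its own discussion.

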DXM has been used in previous research and have been shown to suppress pain symptoms. An example of this previous research comes from Morel et.al. by which low dose DXM was administered and evaluated pain and cognitive function in rats with spinal cord injuries. This animal model demonstrated DXM has a favorable impact on neuropathic pain.

Previous literature has suggested that dextromethorphan at 0.1mg/kg intraperitoneally reduces central inflammation (Chechneva et al., 2011 – link below). This dosage would translate to approximately 8mg for an average U.S. female weighing 166 pounds. Our dosage of 20mg has been adjusted up to account for rapid first-pass metabolism when administered orally.

In this study, we will be administering no more than a daily dose of DXM (20 mg) to observe the possible suppression of symptoms in Fibromyalgia.

References

1) Mease, P. (2005). Fibromyalgia syndrome: review of clinical presentation, pathogenesis, outcome measures, and treatment. *The Journal of Rheumatology*, *75*, 6-21.

4) Jacob Ablin, Lily Neumann, Dan Buskila, Pathogenesis of fibromyalgia – A review, Joint Bone Spine, Volume 75, Issue 3, May 2008, Pages 273-279

Participants (Screening and Selection)

15 participants with fibromyalgia (FM) will be recruited into this study.

- Sex: Female
- Race/Ethnicity: Any
- Age: 23-65
- Health status: 15 individuals with Fibromyalgia

Inclusion Criteria

- 1. Age 18-65, inclusive;
- 2. Meet the 1994 Case Definition criteria for CFS (assessed through semi-structured interview and the DePaul University Fatigue Questionnaire) (attachment #7) & the Fibromyalgia criteria as outlined by American College of Rheumatology (2010).
 - a. Severe chronic fatigue ≥6 consecutive months not due to ongoing exertion or other medical condition associated with fatigue;
 - b. Fatigue interferes with daily activities and work (;
 - c. Reports \geq 4 symptoms that started with or after the fatigue, from:
 - i. Post-exertion malaise >24 hours;
 - ii. Unrefreshing sleep;

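### The primary GEE test at p<0.05 rests on at most 15 planned participants, with no variance estimator, reference distribution or small-sample correction stated; an uncorrected robust Wald z would have a type I error of about 7.9%

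*SAP*

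**What the plan says.** The SAP compares daily general pain over the last four weeks of placebo with the last four weeks of DXM. Scores are centred on each participant's own mean, and a GEE is fitted with study condition as predictor, "assuming the autoregressive correlation structure and normal distributions. The grouping variable was subject ID. Significance of the parameter estimates was assumed at p<0.05". SAS 9.4 is named, but no procedure or option. No test statistic, variance estimator, degrees of freedom or small-sample correction is given.

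On normality it says only "Normality testing was performed with Shapiro–Wilk tests". It does not say which quantity is tested or what follows if normality fails. The approach carries over: "The secondary outcome (self-reported physical activity) was tested using the same GEE approach". Four exploratory outcomes get separate GEEs.

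The Protocol, under Participants (Screening and Selection), states: "15 participants with fibromyalgia (FM) will be recruited into this study". Under Visits 4 and 5 it states: "If any participant has experienced serious/severe adverse events the participant will be terminated from the study". The number analysed could therefore fall below 15; neither document gives it.

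**The concern.** GEE inference is justified as the number of clusters grows, not as the number of records per cluster grows. With "The grouping variable was subject ID", the clusters are participants. Fifty-six diary days per person (28 in each window) do not turn 15 clusters into a large sample.

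The usual sandwich variance is too small with few clusters, and a normal reference ignores the error in estimating it. Both push the p-value down. The stated 5% level might then not hold for the primary outcome, or for the secondary outcome tested in the same way. Because the SAP does not identify the test, a reader who meets a p-value just below 0.05 cannot tell whether it would survive a small-sample correction.

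**Working it through.** The documents give no power, SD or effect-size figure, so there is no figure of the plan's own to reproduce. The check is of the level of the test.

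**Inputs.** n = 15 clusters (Protocol, recruitment target); alpha = 0.05 (SAP), taken as two-sided because sidedness is not stated; n = 12 and n = 10 are assumptions.

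**Step 1: what the GEE reduces to.** With complete data, the condition effect is the mean of the participants' differences d_i between the two windows. The uncorrected sandwich variance is Σ(d_i − d̄)²/n², where the paired t-test has Σ(d_i − d̄)²/[n(n−1)]. Hence robust z = t × √(n/(n−1)), where t has n−1 df if the d_i are normal.

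**Step 2: size of the uncorrected robust Wald z.** Size = 2·P(t_{n−1} > 1.96·√((n−1)/n)).
- n=15: cutoff 1.96 × √(14/15) = 1.894 on 14 df, size 7.91%. The correct cutoff is 2.145.
- n=12: cutoff 1.877 on 11 df, size 8.73%.
- n=10: cutoff 1.859 on 9 df, size 9.59%.

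**Step 3: other readings.**

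| Test | n=15 | n=12 | n=10 |
|---|---|---|---|
| Robust Wald, z | 7.9% | 8.7% | 9.6% |
| Robust SE, t on n−1 df | 5.7% | 5.9% | 6.0% |
| Bias-corrected SE (equals the paired t here), t on n−1 df | 5.0% | 5.0% | 5.0% |
| Robust score test | 4.5% | 4.4% | 4.2% |

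The score statistic is n·t²/(n−1+t²). At n=15 it exceeds 1.96² when |t| > √(3.841 × 14/(15 − 3.841)) = 2.195, which has probability 4.55% on 14 df.

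**Step 4: which results are affected.** The robust-z p that corresponds to a paired-t p of 0.05 is 2·[1 − Φ(t_{.975,n−1}·√(n/(n−1)))]. At n=15 this is 2·[1 − Φ(2.220)] = 0.026; at n=12 it is 0.021 (0.0215) and at n=10 it is 0.017. Going the other way at n=15, robust-z p-values of 0.04, 0.03 and 0.02 become 0.067, 0.055 and 0.041.

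**Step 5: simulation of the described analysis.** Participant-centred scores, AR(1) GEE, 28+28 days, with day-to-day correlation assumed. At n=15 with complete diaries the robust z rejected in 7.9% to 8.5% of null data sets across runs of 4,000 or 5,000 replicates. With about 20% to 25% of days missing at random (assumed) it rejected in 8.0% to 8.9%. Monte Carlo standard error is about 0.4 points, so these agree with the closed form and do not show clear inflation beyond it.

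**Step 6: model-based AR(1) standard errors.** With no participant-specific shift between windows, the simulated size at n=15 was 6.3% to 9.0% at assumed correlations of 0.3 and 0.5. With an assumed SD of 10 for individual shifts against a residual SD of 15, it was about 27% to 38%. The documents give no SD, so these values show only that the choice of estimator matters.

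**Step 7: non-normal differences (assumed shapes, n=15).**

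| Shape | Paired t | Robust z | Sign-flip |
|---|---|---|---|
| Gamma, skewness 1 | 6.1% | 9.0% | 6.2% |
| Exponential | 8.8% | 11.6% | 8.9% |
| t with 3 df | 4.2% | 7.1% | 4.9% |

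The robust z exceeds the paired t by about 3 points in each shape.

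**The case against.** The strongest reply is that this is a gap in reporting, not a demonstrated failure of the 5% level. The SAP names no statistic; 7.9% belongs to one reading, and a robust score test would be slightly conservative. That stands, and the figure is given only conditionally. But the omission does not depend on any reading, and testing the significance of parameter estimates points most naturally to a Wald test.

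The consequence is also narrow: about 3 points, relevant only to p-values between roughly 0.026 and 0.05, in a small study that already states "There were no corrections for multiple comparisons". That stands too. It limits the severity but does not remove the problem, since the plan names a primary outcome and a threshold.

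Three further points are fair:
- The count of 15 is a recruitment plan. The termination rule shows that participants can leave, not that their data are dropped.
- A participant-level t-test weights participants equally, while the GEE pools diary days, so with missing days the two can estimate slightly different averages.
- Every participant takes placebo before DXM. A corrected test therefore restores the level only for the hypothesis of no mean change between the two windows. Attributing that change to the drug is a separate matter.

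**Conclusion.** The concern holds and should be fixed. The SAP leaves the variance estimator, reference distribution and small-sample handling of its primary test unstated, with at most 15 planned clusters.

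The inflation under the uncorrected robust Wald z (7.9% against a nominal 5% at n=15, more if fewer are analysed) assumes two-sided testing, complete diaries and near-normal participant differences. It changes little with random missing days. There is no excess under a robust score test. Under model-based errors there is an excess that cannot be sized from the documents. The trial's actual error rate is therefore unknown until the test is named. The same applies to the secondary outcome; the four exploratory models matter less.

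**What to change.** State the variance estimator, the reference distribution and its degrees of freedom. Make the primary test one of these:
- (a) a one-sample t-test on each participant's DXM-minus-placebo difference in four-week means; or
- (b) the GEE with a bias-corrected sandwich (for example Kauermann-Carroll) and a t reference on participants minus 1 df. The t reference does most of the work (5.7% alone, 5.0% with the bias correction).

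Option (b) keeps the GEE's weighting by diary day if that is the intended average.

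Both options need near-normal differences. Say that the Shapiro-Wilk check applies to the participant differences, and add a sign-flip test as a sensitivity analysis. That test is exact when the differences are symmetric about zero under the null, but it does not cure strong skew. Use the same method for the secondary outcome and, for consistency, the exploratory ones. Report the number of participants analysed.

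The cost is one or two sentences and slightly larger p-values. The SAP is mostly in the past tense; if results already exist, six models (one primary, one secondary, four exploratory) and one sensitivity test need re-running, labelled as a later correction.
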